Subjects who receive protocol-defined glucocorticoid Rescue Therapy, initiate glucocorticoids (other than inhaled) after Baseline without qualifying for Rescue Therapy, fail to complete glucocorticoid tapering by Week 6, or who increase doses of or initiate treatment with aminosaliculates or immunomodulators during the Induction Period will be considered non-responders and will be re-randomized into the Re-Induction Period. All subjects who fulfill the clinical response AND/OR endoscopic response (per local read) definition at Week 12 of the Re-Induction Period will be re-randomized into the Maintenance Period.

The criteria for inadequate response are the following:

- Induction Period: Presence of clinical symptoms defined as CDAI ≥ 220 and not achieving a decrease in CDAI ≥ 35 points from Baseline of the Induction Period.
- Maintenance Period: Presence of clinical symptoms defined as CDAI ≥ 220 and an increase in CDAI ≥ 70 points from Baseline of the Maintenance Period.
- And, for both the Induction Period and Maintenance Period, presence of at least 1 of the following objective markers of inflammation:
 - hs-CRP \geq ULN, and worse than the lowest value assessed during the study, or
 - FCP ≥ 250 $\mu\text{g/g}$, and worse than the lowest value assessed during the study, or
 - SES-CD, excluding the narrowing component, ≥ 6 (≥ 4 for isolated ileal disease), as scored by the site investigator at an endoscopy.

The last available values for hs-CRP and FCP will be used for assessment of inadequate response.

Use of Rescue Therapy in subjects who qualify is at the investigator's discretion and not mandatory.

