At Week 12 of the Induction Period, subjects who are categorized as clinical non-responders and endoscopic non-responders (per local read) will be re-randomized into the Re-Induction Period. Subjects who receive Rescue Therapy, fail to complete glucocorticoid tapering by Week 6, or increase doses of or initiate treatment with aminosalicylates or immunomodulators in the Induction Period will be considered non-responders, regardless of clinical response or endoscopic response (per local read) per the definitions above at Week 12 and will be re-randomized in a 1:1 ratio into 2 ABBV-154 treatment groups in the 12-Week Re-Induction Period as follows:

- Re-Induction Group 1: Loading dose of 300 mg IV at Week 0, followed by 230 mg SC at Week 2 and EOW;
- Re-Induction Group 2: Loading dose of 600 mg IV at Week 0, followed by 530 mg SC at Week 2 and EOW.

Subjects who achieve clinical response AND/OR endoscopic response (per local read) at Week 12 of the Re-Induction Period will be re-randomized into the Maintenance Period as described above for subjects achieving clinical response AND/OR endoscopic response

(per local read) after Week 12 of the Induction Period. Subjects who do not achieve either clinical response or endoscopic response (per local read) after the Re-Induction Period will be discontinued and will have a follow-up visit scheduled 70 days after last study drug administration.

To determine endoscopic response status for re-randomization into the Maintenance Period, the SES-CD score per local read at Week 12 of the Induction/Re-Induction Period and the SES-CD score per central read at Baseline will be used. In the case of missing data where either clinical response or endoscopic response cannot be determined, subjects will be considered non-responders for the re-randomization criteria evaluation.

[figure not shown]
Subjects who have an inadequate response at or after Week 4 in the Maintenance Period will be eligible to receive Rescue Therapy with a single dose of ABBV-154 600 mg IV followed by ABBV-154 230 mg SC EOW. Subjects who have received rescue therapy with ABBV-154 for at least 4 weeks and who continue to demonstrate inadequate response may receive additional Rescue Therapy with oral glucocorticoids, aminosalicylates, or immunomodulators.

The last dose of study drug will be given at Week 38 of the Maintenance Period. A follow-up visit will be scheduled 70 days after the last study drug administration.

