10.2.1 Treatment-Emergent Adverse Events

Induction Period (SA1 population): TEAEs for the Induction Period are defined as events that begin either on or after the first dose of the study drug in the Induction Period and until (i) the first dose of study drug in the Re-Induction Period (if applicable), or (ii) until first dose of study drug in the Maintenance Period (if applicable), or (iii) within 70 days after the last dose administration of the study drug in the Induction Period, whichever is earlier.

Re-Induction Period (SA2 population): TEAEs for the Re-Induction Period are defined as events that begin either on or after the first dose of the study drug in the Re-Induction Period and until (i) first dose of study drug in the Maintenance Period (if applicable), or (ii) within 70 days after the last dose administration of the study drug in the Re-Induction Period, whichever is earlier.

Maintenance Period (SA3 population): TEAEs for the Maintenance Period are defined as events that begin either on or after the first dose of the study drug in the Maintenance Period and until (i) within 70 days after the last dose administration of the blinded study drug in the Maintenance Period, or (ii) initiation of ABBV-154 rescue therapy, whichever is earlier.

ABBV-154 Rescue Therapy (SA-RES population): TEAEs for the ABBV-154 rescue therapy are defined as events that begin either on or after the first dose of the ABBV-154 rescue therapy in the Maintenance Period and until 70 days after the last dose administration of the study drug in the Maintenance Period.

All ABBV-154 (SA-ALL154 population): TEAEs for "All ABBV-154" are defined as events that begin either on or after the first dose of ABBV-154 and within 70 days after the last dose of ABBV-154 in the study. Events that begin when subjects on Placebo will be not included.

Safety analyses from combined periods:

Induction Period + Re-Induction Period ABBV-154 (SA-IN2 population): TEAEs for "Induction Period + Re-Induction Period ABBV-154" (SA_IN2) are defined as events that begin either on or after the first dose of ABBV-154 in the Induction Period and until (i) first dose of study drug in the Maintenance Period (if applicable), or (ii) within 70 days after the last dose of study drug in the study, whichever is earlier.

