10.3 Analysis of Laboratory Data

Data collected from central and local laboratories, including additional laboratory testing due to an SAE, will be used in the analyses. Baseline values collected for SAE-related laboratory assessments on or before the first dose of study drug will be excluded. Data collected more than 70 days after the last dose of study drug of the analysis period (See Section [10.2.1](#)) for the corresponding analysis populations will be excluded.

The clinical laboratory tests defined in the protocol (e.g., hematology and clinical chemistry) will be summarized.

Analysis of Quantitative Laboratory Parameters

Each laboratory variable will be summarized at all time points (starting at baseline) with the number of observations, mean, standard deviation, median, minimum and maximum

for non-missing observations. The change from Baseline at each applicable post-baseline visit will be summarized for selected laboratory variables, with the number of observations, baseline mean, and visit mean. The mean, standard error, and 95% CI will be presented for the change from Baseline for each treatment group.

For each period, treatment group differences for the changes from baseline will be analyzed using a one-way Analysis of Variance (ANOVA) model with treatment as a fixed factor and 95% CI for treatment difference will be presented for selected laboratory parameters.

Shift Table Analyses

Changes in laboratory parameters will be tabulated using shift tables categorized as low, normal, or high based on the normal ranges of the laboratory used for each sample. A shift table summarizes shifts from baseline to minimum and maximum values (based on normal range) will be created. A similar shift table will be provided to summarize shifts from baseline to the final post-baseline value.

Potentially Clinically Significant Laboratory Values

The criteria for potentially clinically significant laboratory values will be determined by CTCAE criteria of Grade 3, Grade 4 and \geq Grade 3, with a grade worsening compared to baseline. Toxicity grading scale is based on National Cancer Institute Common Toxicity Criteria (NCI CTC) AE version 5.0. The number and percentage of subjects meeting the criteria for potentially clinically significant laboratory values will be summarized by treatment group. Listings of subject-level laboratory data will be provided for subjects meeting the criteria.

Assessment of Liver Elevations

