The liver-specific laboratory tests include the serum glutamic pyruvic transaminase (SGPT/ALT), serum glutamic-oxaloacetic transaminase (SGOT/AST), alkaline phosphatase (ALP), and total bilirubin (TBL). The frequencies and percentages of

subjects with post baseline liver specific function test values that meet the following criteria of potential clinical interest will be summarized by treatment group:

- $ALT > 3 \times ULN$
- $ALT > 5 \times ULN$
- $ALT > 10 \times ULN$
- $ALT > 20 \times ULN$
- $AST > 3 \times ULN$
- $AST > 5 \times ULN$
- $AST > 10 \times ULN$
- $AST > 20 \times ULN$
- $TBL > 1.5 \times ULN$
- $TBL > 2 \times ULN$
- $ALP > 1.5 \times ULN$
- $ALT \text{ and/or } AST > 3 \times ULN \text{ and } TBL > 1.5 \times ULN$
- $ALT \text{ and/or } AST > 3 \times ULN \text{ and } TBL > 2 \times ULN$
- $ALT > 3 \times ULN \text{ and } TBL > 1.5 \times ULN$
- $ALT > 3 \times ULN \text{ and } TBL > 2 \times ULN,$

where ULN is the upper normal limit. The maximum ratio relative to the ULN will be used to determine if subjects meet any of the criteria listed above.

A listing of subjects, defined as those meeting the following criteria will also be provided:

- $ALT \text{ and/or } AST > 3 \times ULN \text{ and/or } ALP > 1.5 \times ULN \text{ and } TBL > 1.5 \times ULN$

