10.4 Analysis of Vital Signs

Vital sign measurements of systolic and diastolic blood pressure, pulse rate, body weight, respiratory rate and body temperature will be summarized. Data collected more than 70

days after the last dose of study drug of the analysis period (See Section 10.2.1) for the corresponding analysis populations will not be included.

Each vital sign variable will be summarized at all time points (starting with Baseline) with the number of observations, mean and standard deviation, median, minimum and maximum for non-missing observations. Change from Baseline at each applicable post-baseline visit will be summarized for each vital sign variable, with the number of observations, Baseline mean, and visit mean. The mean, standard error, and 95% CI will be presented for the change from Baseline for each treatment group.

For each period, treatment group differences for changes from Baseline will be analyzed using a one-way Analysis of Variance (ANOVA) with treatment as a fixed factor and 95% CI for treatment difference will be presented for each vital sign variable.

Vital sign variables will be evaluated based on potentially clinically important (PCI) criteria (See ABBV-154 PSSAP). For each vital sign PCI criterion, the number and percentage of subjects who have a vital sign value meeting the criteria will be summarized. Listings will be provided to summarize subject-level vital sign data for subjects meeting PCI criteria.

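### Maintenance adverse-event follow-up ends at efficacy-triggered rescue, but subject-level harm percentages, and in part the planned event rates, do not allow for unequal follow-up between arms

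*SAP*

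**What the plan says.** - **Adverse-event window (SAP 10.2.1).** For the Maintenance safety population (SA3), a TEAE counts until "within 70 days after the last dose administration of the blinded study drug in the Maintenance Period, or (ii) initiation of ABBV-154 rescue therapy". The first of these two dates applies. Later events go to a separate population of rescued subjects (SA-RES).
- **Length of the window (SAP 2.2).** "The last dose of study drug will be given at Week 38 of the Maintenance Period". An unrescued completer is therefore followed to 70 days after Week 38.
- **Access to rescue (SAP 2.2, Protocol 5.4).** "Subjects who have an inadequate response at or after Week 4 in the Maintenance Period will be eligible to receive Rescue Therapy". The symptom criterion is "Presence of clinical symptoms defined as CDAI ≥ 220 and an increase in CDAI ≥ 70 points from Baseline of the Maintenance Period", together with at least one objective marker of inflammation. Giving rescue to a subject who qualifies is left to the investigator.
- **Adverse-event summaries (SAP 10.2.2 to 10.2.6).** Subject-level results are numbers and percentages. Event rates per 100 patient-years are also planned for the overview categories, by SOC and PT, and for AESIs. Section 10.2.4 counts events in the numerator. It takes exposure as first dose to last dose plus 70 days, with no stop at rescue.
- **Laboratory and liver (SAP 10.3).** "The number and percentage of subjects meeting the criteria for potentially clinically significant laboratory values will be summarized by treatment group". For liver criteria, "The maximum ratio relative to the ULN will be used to determine if subjects meet any of the criteria" listed.
- **Vital signs (SAP 10.4).** For each criterion of potential clinical importance, "the number and percentage of subjects who have a vital sign value meeting the criteria will be summarized".
- **Cut-off for laboratory and vital-sign data.** Sections 10.3 and 10.4 drop values more than 70 days after the last dose of the analysis period, with a cross-reference to 10.2.1. Neither names rescue.

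**The concern.** Follow-up for harm is cut short by an efficacy outcome. If ABBV-154 maintains response better than placebo, placebo subjects should reach rescue more often, and their harm windows will be shorter on average. The percentage with at least one event then comes out lower on placebo even when the underlying hazard is the same. Threshold criteria of the ever-met or maximum-value kind behave the same way if their data also stop at rescue, because a subject rescued early has fewer scheduled measurements.

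This matters because Maintenance is the only long-term placebo comparison. Induction is controlled for 12 weeks, and Re-Induction has no placebo arm. Protocol 4.2 says the Maintenance regimens are meant to support selection of Phase 3 maintenance doses, and the safety topics include glucocorticoid effects and adrenal insufficiency. A false excess on ABBV-154 could weigh in that choice.

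**Working it through.** **What the plan quantifies.** No adverse-event rate, rescue rate or follow-up by arm is stated. The nearest figure is power for Week 40 endoscopic response: 40 per group, 11% versus 37%, two-sided alpha 0.1, stated as more than 80%. It reproduces at 87.1%. It does not give a rescue rate.

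**Inputs from the documents.** Full window = 38 × 7 + 70 = 336 days (48 weeks). Earliest rescue is Week 4 (day 28).

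**Assumptions.** The hazard h is constant and identical in both arms, with 10% incidence over 336 days: h = −ln(0.9)/336 = 0.0003136 per day, or 11.45 per 100 patient-years. A fraction f of each arm is rescued at day d = 56 (Week 8) or 112 (Week 16). There is no other dropout.

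**Formulas.**
- Mean window = f·d + (1 − f)·336.
- Crude incidence = f·(1 − e^(−h·d)) + (1 − f)·0.10, where 1 − e^(−h·d) is 1.74% at d = 56 and 3.45% at d = 112.

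**Crude percentages.**

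| Rescued, placebo / ABBV-154 | Window ratio, placebo : ABBV-154 (Week 8; Week 16) | False crude ratio, ABBV-154 : placebo (Week 8; Week 16) |
|---|---|---|
| 30% / 30% | 1.00; 1.00 | 1.00; 1.00 |
| 30% / 15% | 0.86; 0.89 | 1.16; 1.12 |
| 50% / 20% | 0.70; 0.77 | 1.42; 1.29 |
| 60% / 30% | 0.67; 0.75 | 1.49; 1.32 |
| 60% / 15% | 0.57; 0.67 | 1.74; 1.49 |

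Worked example, 50% / 20% at Week 16:
- Placebo: 0.5 × 3.45% + 0.5 × 10% = 6.7%.
- ABBV-154: 0.2 × 3.45% + 0.8 × 10% = 8.7%.
- At 40 per group this is 2.7 versus 3.5 subjects.

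Spreading rescue uniformly over days 28 to 280, with a true rate of 10 per 100 patient-years, gives a false crude ratio of 1.06 at 30% / 20%, 1.22 at 50% / 20% and 1.42 at 70% / 20%.

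**Planned event rates, same worked example.** Events accrue over mean windows of 224 days (placebo) and 291.2 days (ABBV-154). The 10.2.4 denominator can be read in two ways.
- *Last blinded dose plus 70 days.* If the last blinded dose is 14 days before rescue, a rescued subject contributes 112 − 14 + 70 = 168 days. The denominators are 0.5 × 168 + 0.5 × 336 = 252 and 0.2 × 168 + 0.8 × 336 = 302.4 days. The rates are 11.45 × 224/252 = 10.2 and 11.45 × 291.2/302.4 = 11.0 per 100 patient-years, ratio 1.08.
- *Last dose of any study drug, at Week 38, plus 70 days.* The denominator is 336 days in both arms. The rates are 7.6 and 9.9, ratio 1.30.
- *Patient-years stopped at rescue.* The rate is 11.45 in both arms, ratio 1.00.

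With uniformly spread rescue at 50% / 20%, the two readings give 1.07 and 1.22. The planned rates therefore leave part or all of the distortion in place, in the same direction as the percentages.

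**The case against.** Several points against the concern stand.

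- **Crude percentages are not the only comparison.** A reader might infer that they are. Event rates are planned for every overview category, and treatment duration is tabulated by arm (SAP 6.0), so unequal follow-up would be visible. For rare SAEs and AESIs, event and subject counts differ little. What remains is the mismatch between numerator and denominator at rescue.
- **More rescue on placebo is an expectation.** It is tempting to read it from the planning rates (89% versus 63% not in endoscopic response). Those are endoscopic rates. Rescue needs CDAI worsening plus an inflammatory marker and is discretionary. With equal rescue the distortion vanishes.
- **Laboratory and vital-sign effects are not inseparable from longer observation.** A reader might conclude that they are. Change from Baseline by visit is planned, with between-group confidence intervals for selected laboratory parameters and all vital signs. These means do not rise with the number of measurements.
- **The laboratory part is conditional.** The SAP version history names rescue as the cut-off for TEAEs, but only the 70-day limit for laboratory and vital-sign data. If values after rescue are kept, the shortage of placebo measurements largely disappears.
- **The size is small in subjects, and no adverse-event test is planned.** That is true, but descriptive percentages by arm are still what readers will compare.
- **The remedy has its own assumption.** Randomised Maintenance placebo subjects have already received ABBV-154. If events cluster early or carry over, a constant-hazard rate would overstate risk in an arm cut off early.

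**Conclusion.** The concern holds in a limited form. SA3 adverse-event follow-up ends at an efficacy-triggered event, subject-level percentages ignore this, and the planned event rates correct it only partly. For laboratory, liver and vital-sign threshold criteria nothing adjusts for time. That matters only if SA3 values end at rescue, and the visit-wise summaries mitigate it in part.

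Under an identical hazard of 10% over 48 weeks and rescue at Week 8 or 16, the false crude ratio runs from 1.00 with equal rescue, through 1.12 to 1.49 when placebo rescue is 2 to 2.5 times that on ABBV-154, to about 1.74 at 60% versus 15% at Week 8. The rescue fractions and times are assumptions, and the sums ignore other dropout. At about 40 per group the worked example is 0.8 of a subject. This is a worthwhile low-cost improvement. It does not show that the planned safety comparison is invalid, and ending the blinded window at rescue is reasonable in itself.

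**What to change.** In SAP 10.2.2, 10.2.6, 10.3 and 10.4, for the re-randomised Maintenance arms:

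- Add subjects with a first event per 100 patient-years at risk. Time runs from the first Maintenance dose to the first event or the end of the 10.2.1 window. Give rate differences versus placebo.
- Apply this to SAEs, AESIs, potentially clinically significant laboratory values, liver criteria and vital-sign criteria.
- Leave out of this comparison the Induction-placebo responders assigned without randomisation to 80 mg, who are also in SA3.
- Show the rescue proportion and mean follow-up by arm.
- Label the crude percentages as not adjusted for follow-up.

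The cost is SAP wording and some extra table columns from dates already collected. The tables become longer. The rates assume a constant hazard, which may fail if events cluster early or carry over from induction ABBV-154, so the SAP should state that limitation.

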4 INVESTIGATIONAL PLAN

4.1 Overall Study Design and Plan

This is a randomized, double-blind, placebo-controlled Phase 2b study to assess the safety, tolerability, PK, PD, immunogenicity, and efficacy of ABBV-154 in subjects with moderately to severely active CD who had inadequate response to or were intolerant of prior biologics. The enrollment for subjects with prior adalimumab use is capped at approximately 30% of the total enrolled subjects. The study comprises 3 periods: a 12-Week Double-Blind Placebo-Controlled Induction Period, a 12-Week Double-Blind Re-Induction Period (for subjects considered to be clinical non-responders and endoscopic non-responders), and a 40-Week Double-Blind Placebo-Controlled Maintenance Period.

At the Baseline Visit of the Induction Period, approximately 265 subjects will be randomized in a 1:1:1:1:1 ratio into 4 ABBV-154 treatment groups or placebo:

1. Induction Group 1: Loading dose of 150 mg IV at Week 0, followed by 80 mg subcutaneous (SC) at Week 2 and every other week (EOW);
2. Induction Group 2: Loading dose of 300 mg IV at Week 0, followed by 230 mg SC at Week 2 and EOW;
3. Induction Group 3: Loading dose of 600 mg IV at Week 0, followed by 530 mg SC at Week 2 and EOW;
4. Induction Group 4: Loading dose of 600 mg IV at Week 0, followed by 530 mg SC at Weeks 4 and 8, and placebo at Weeks 2, 6, and 10; and
5. Induction Group 5: Matching placebo (IV and SC).

At Week 12 of the Induction Period, subjects achieving clinical response, defined as a decrease in CDAI ≥ 100 points from Baseline (CR100) AND/OR endoscopic response (per local read) will receive treatment in the 40-Week Maintenance Period as follows:

1. Induction Group 1: Re-randomized in a 1:1 ratio to receive ABBV-154 80 mg SC EOW or matching placebo;
2. Induction Groups 2 to 4: Re-randomized in a 1:1:1 ratio to receive ABBV-154 80 mg SC EOW, ABBV-154 230 mg SC EOW, or matching placebo;
3. Induction Group 5: ABBV-154 80 mg SC EOW.

At Week 12 of the Induction Period, subjects who are categorized as clinical non-responders and endoscopic non-responders (per local read) will be re-randomized into the Re-Induction Period.

Subjects who demonstrate inadequate response at or after Week 8 in the Induction Period may receive Rescue Therapy with oral glucocorticoids as defined in Section 5.4.

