Management of Demyelinating Disease

Subjects must be discontinued from study drug with new onset of symptoms and/or radiographic evidence of central nervous system demyelinating disease (including multiple sclerosis), optic neuritis, or peripheral demyelinating disease (including Guillain Barré syndrome).

Management of Hypertension

Subjects should be closely monitored for the development of hypertension. Investigators should consider stopping the study drug if hypertension is not successfully controlled under standard of care.

Management of Hyperglycemia

Subjects should be closely monitored for the development of hyperglycemia. Investigators should manage the hyperglycemia with appropriate standard of care.

Management of Glucocorticoid Induced Adrenal Insufficiency

Subjects should be closely monitored for signs and symptoms of adrenal insufficiency (e.g., nausea, vomiting, lightheadedness, pale skin, unexplained weight loss, low blood pressure, electrolyte abnormalities [e.g., hyponatremia < 135 mmol/L, hyperkalemia > 5.5 mmol/L]) and if adrenal insufficiency is suspected, further assessment and management should follow local standard of care, which may include measuring cortisol levels and/or ACTH stimulation testing at a local laboratory. Glucocorticoid therapy with physiologic doses should be considered. After withdrawal of glucocorticoid therapy, adrenal insufficiency may persist for months; therefore, glucocorticoid therapy should be considered in any situation of stress (e.g., serious infection) occurring or in the months following withdrawal of study drug.

Management of COVID-19

Subjects should be closely monitored for COVID-19. Study drug should be interrupted if a subject has a confirmed diagnosis of COVID-19. Consider the interruption of study drug in subjects with signs and/or symptoms and suspicion of COVID-19.

Management of Select Laboratory Abnormalities

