6.0 Study Drug Duration and Compliance

For the safety populations (SA1, SA2 and SA3), duration of treatment will be summarized by each treatment group for each period. Duration of treatment is defined for each subject as last dose date of blinded study drug minus first dose date + 14. Duration of treatment

will be summarized for each treatment group using the number of subjects treated, mean, standard deviation, median, minimum, and maximum. In addition, the number and percentage of subjects in the following treatment duration intervals will be summarized.

Induction/Re-Induction Period: < 2 weeks [14 days], ≥ 2 weeks [14 days], ≥ 4 weeks [28 days], ≥ 8 weeks [56 days], and ≥ 12 weeks [84 days]

Maintenance Period: < 2 weeks [14 days], ≥ 2 weeks [14 days], ≥ 4 weeks [28 days], ≥ 8 weeks [56 days], ≥ 12 weeks [84 days], ≥ 24 weeks [168 days], ≥ 36 weeks [252 days], and ≥ 40 weeks [280 days]

Treatment compliance will be summarized by treatment group for each period for the safety population. Treatment compliance is defined as the number of infusions/injections actually taken divided by the number of infusions/injections that should have been taken. Percent compliance will be summarized.

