10.2.4 Treatment-Emergent Adverse Events per Patient-Years of Exposure

TEAEs will be summarized by event rate per 100 subject years, defined as

$$100 \times \frac{\text{Number of TEAEs}}{\text{Total Patient Years}}$$

where total patient years is defined as the sum of the study drug exposure of all subjects, normalized by 365.25, and rounded to 1 decimal place. Note that one event per preferred term per day per subject will be counted in the calculation of the number of AEs (i.e., a preferred term will not be counted twice on the same day for the same subject).

The TEAE rates per 100 patient-years of exposure will be provided for each AE category in the AE overview summary (defined in Section 10.2.2) and for TEAE summary by SOC and PT.

The study drug exposure for each safety population is defined as last dose date plus 70 days, minus the first dose date. For SA-All154 safety population, the duration when subjects on Placebo will not be included in the calculation.

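### The all-ABBV-154 safety set drops events and time on Maintenance placebo even within 70 days of the last ABBV-154 dose, removing up to 56 of those 70 days for subjects re-randomised to placebo

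*SAP*

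**What the plan says.** For SA-ALL154, SAP 10.2.1 counts events from the first ABBV-154 dose to "within 70 days after the last dose of ABBV-154 in the study". The next sentence reads "Events that begin when subjects on Placebo will be not included". SAP 10.2.4 defines exposure as the span from first dose to last dose plus 70 days, and then says "For SA-All154 safety population, the duration when subjects on Placebo will not be included in the calculation".

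In Protocol 4.1, responders from Induction Groups 2 to 4 are "Re-randomized in a 1:1:1 ratio to receive ABBV-154 80 mg SC EOW, ABBV-154 230 mg SC EOW, or matching placebo". Group 1 responders are split 1:1 between 80 mg and placebo. Responders from Re-Induction enter the same Maintenance scheme.

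Protocol 6.2 warns that "After withdrawal of glucocorticoid therapy, adrenal insufficiency may persist for months", and it also refers to the months after study drug is withdrawn. SAP Appendix G lists adrenal insufficiency as an adverse event of special interest (AESI).

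**The concern.** The two sentences in SAP 10.2.1 pull against each other. Induction placebo time comes before the first ABBV-154 dose, so it is already outside the SA-ALL154 window. The exclusion therefore acts on Maintenance placebo time, and part of that time lies inside the 70 days that the SAP itself treats as attributable to ABBV-154.

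The same post-dose day is then classified differently according to what the subject does next. Day 30 after a Week 10 dose counts as ABBV-154 for a subject who stops the drug. It does not count for a responder re-randomised to placebo.

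The payload is a glucocorticoid receptor modulator, so the time removed is the early withdrawal period of a drug for which withdrawal effects are a named safety topic. An event caused by withdrawal in that time would be absent from the pooled ABBV-154 counts and would be labelled a placebo event.

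**Working it through.** **Calendar.** The documents give no figure for the days removed, so the check starts with the calendar. The Protocol synopsis gives a maximum treatment duration of 448 days, and (12 + 12 + 40) × 7 = 448, so the periods run back to back. SAP 6.0 defines treatment duration as "last dose date of blinded study drug minus first dose date + 14". For a last dose at Week 10 this gives 70 + 14 = 84 days = Week 12, which is Maintenance Week 0. Nominal visit days are assumed.

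**Last active dose (Protocol 4.1).**
- Induction Groups 1 to 3 and both Re-Induction groups: Week 10. For example, Group 2 has "Loading dose of 300 mg IV at Week 0, followed by 230 mg SC at Week 2 and EOW", and the activity schedule shows no Induction dose at Week 12.
- Induction Group 4: Week 8, because it receives "530 mg SC at Weeks 4 and 8, and placebo at Weeks 2, 6, and 10".

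**Days removed** = 70 − 7 × (12 − week of last active dose).
- Last active dose at Week 10: 70 − 14 = 56 days (80% of the window).
- Last active dose at Week 8: 70 − 28 = 42 days (60%). This becomes 56 only if Group 4's Week 10 placebo injection is read as being on placebo.

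**Effect of rescue.** ABBV-154 rescue is possible from Maintenance Week 4 and ends the placebo time. Rescue at Week 4 leaves 28 days removed in every group, and rescue at Week 6 leaves 42. From Week 8 on, the full 56 days (42 for Group 4) are removed.

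**Subjects.** With 53 per group and an assumed common responder rate r, the number going from ABBV-154 Induction to placebo is 53r × (1/2 + 3 × 1/3) = 79.5r. The documents give no rate for the combined clinical or endoscopic response. Taking r = 0.4 to 0.6 as an assumption gives 79.5 × 0.4 = 32 to 79.5 × 0.6 = 48 subjects.

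**Patient-years removed.** 53r × [(1/2 + 2/3) × 56 + (1/3) × 42] / 365.25 = 53r × 79.33 / 365.25 = 11.5r, or 4.6 to 6.9 for the same range. Group 4 supplies (1/3)/(3/2) = 22% of these subjects, and the mean cut is 79.33/1.5 = about 53 days. This leaves out Re-Induction entrants and ignores early rescue. As a cross-check that does not use r, 40 placebo subjects (the minimum per group in Protocol 7.10) give 40 × 42/365.25 = 4.6 to 40 × 56/365.25 = 6.1 patient-years.

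**Where the events go (SAP 4.0 and 10.2.1).**
- SA1, SA2 and SA-IN2 stop at the first Maintenance dose, so they do not contain them.
- SA-INMN and SA-IN2MN need an ABBV-154 dose in Maintenance, so they omit non-rescued placebo subjects. A rescued subject meets the SA-INMN condition, and that set's window runs up to rescue with no placebo exclusion, so these events are counted there.
- SA3 contains them, in the placebo group.

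**Direction of the rate.** Let the retained data hold E events in T years and the removed time e events in t years. Restoring the time changes E/T to (E + e)/(T + t), which is higher only if e/t > E/T. The documents give no event rates, so the direction is unknown. The count can only rise or stay the same.

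**The case against.** The best defence is that the exclusion is deliberate and has a proper use. The version history for SAP 2.0 records it as a clarification. For a placebo subject who is later rescued, the last ABBV-154 dose is a rescue dose. Without the exclusion, all the placebo time before rescue would count as ABBV-154. This stands, and it means the sentence should be qualified, not deleted.

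The events are also not hidden. SA3 tabulates them, adrenal insufficiency has its own eCRF and AESI summary, systemic glucocorticoid events are adjudicated, and the DMC sees unblinded safety data. This too stands. It limits the issue to attribution in a pooled, descriptive Phase 2 summary.

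Four stronger readings are tempting, but the documents do not support them:
- **That the pooled rate is understated.** SAP 10.2.4 removes the matching time, so numerator and denominator are cut together.
- **That every re-randomised subject loses 56 days.** Subjects re-randomised to ABBV-154 lose nothing, Group 4 loses 42 days, and early rescue shortens the loss.
- **That adrenal insufficiency is expected to arise in the removed days.** Protocol 6.2 speaks of how long it may persist and gives no onset time. Onset on drug, or before placebo starts, is already counted.
- **That this sentence biases the SA3 comparison.** Placebo-labelled withdrawal events in SA3 follow from the re-randomised withdrawal design and from SA3's own rule. Changing SA-ALL154 would not alter them.

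**Conclusion.** The point holds in limited form. The placebo exclusion overrides the SAP's own 70-day window for subjects re-randomised from ABBV-154 to Maintenance placebo. It removes 56 days after Induction Groups 1 to 3 or either Re-Induction group, 42 days after Induction Group 4, and fewer with early rescue. For non-rescued subjects, no ABBV-154-labelled set recovers the events.

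The size, about 32 to 48 subjects and 4.6 to 6.9 patient-years, rests on an assumed 40% to 60% responder rate that is equal across the four active groups, on nominal visit days and on no early rescue. Re-Induction entrants would add to it. ABBV-154 event counts are understated only if events occur in that time, and the effect on the rate is undetermined. This is an inexpensive improvement to attribution, and nothing here shows that the trial's safety conclusions would be wrong.

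**What to change.** In SAP 10.2.1, for SA-ALL154, include events that begin on placebo up to 70 days after the most recent ABBV-154 dose before the event. Exclude only placebo time beyond that, until any ABBV-154 rescue dose. Tying the rule to the most recent preceding dose, and not to the last dose in the study, keeps later pre-rescue placebo time out. Apply the same rule to person-time in SAP 10.2.4, and state that Group 4's interspersed placebo injections do not count as time on placebo.

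In SA3, show placebo-group events, at least the AESIs, separately for within and after 70 days of the last ABBV-154 dose.

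The cost is SAP wording, one derivation flag and a few more tables. ABBV-154 event counts may rise slightly. Trial conduct, data collection and the efficacy analyses are unaffected.
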